15.2.3. INR Grading

The DAIDS Toxicity Table includes grading for subjects not on anticoagulant therapy. As many of the subjects will be on anticoagulant therapy, these subjects’ INR values will not be graded. Additionally, reporting of AEs will be based on the following guidelines:

- If a subject is on anticoagulant therapy, INR in the 2.0-<3.0 times the upper limit of normal is expected and an AE does not need to be reported. However, an INR 3.0 or more times the upper limit of normal is reported in the context of a clinical syndrome.

- If a subject is not on anticoagulant therapy or on Low Molecular Weight Heparin (LMWH) like Enoxaparin (Lovenox) and has any INR values at least 2.0 times the upper limit of normal (grade 3+) then an AE for INR should be reported. Note that abnormal INR values should be reported as part of a clinical syndrome (e.g., coagulopathy secondary to sepsis; GI bleed; multi-organ failure, etc.) and not reported as a separate AE.

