9.1.2. Prior and Concomitant Medications

Medication history (concomitant medications) includes a review of all current medications and medications taken within 7 days prior to enrollment through approximately Day 15 or early termination (if Day 15), whichever occurs first.

Summaries of medications that were started prior to dosing and continued at the time of dosing or started after dosing while on study will be presented by WHO Drug Level 1 and 2 Codes, actual baseline ordinal score, and treatment group ([Table 57](#)). Summaries of overall use of medications/therapies of interest listed in Section [6.4](#) that were started prior to dosing and continued at the time of dosing or started after dosing while on study as well as use by select study days will also be generated ([Table 58](#) and [Table 59](#)).

Individual subject listings will be presented for all concomitant medications ([Listing 9](#)), corticosteroid use ([Listing 10](#)), and medications of interest ([Listing 11](#)).

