9.6. Clinical Laboratory Evaluations

Clinical safety laboratory adverse events are collected Day 1, 3, 5, 8, 11 and Day 15 and 29 if able to return to clinic or still hospitalized. Parameters evaluated include white blood cell count, absolute neutrophil count, eGFR, platelet count, hemoglobin concentration, creatinine, glucose, total bilirubin, ALT, AST, INR, d-dimer, and CRP. Laboratory safety parameters will be graded according to the Division of AIDS (DAIDS) Table for Grading the Severity of Adult and Pediatric Adverse Events, version 2.1 (July 2017). For sites that do not

report an upper (lower) limit for the value of a laboratory parameter, the median of the reported upper (lower) limits across the other sites will be used. Medians and calculated LLN/ULN used if any, will be documented in the ADaM documentation. Vitamin D is collected on Day 1 and is not graded, but results will be summarized.

The distribution of Grade 3 and 4 chemistry and hematology laboratory results by maximum severity, time point, actual baseline ordinal score and treatment group will be presented ([Table 88](#)). Treatment-emergent laboratory abnormalities will be summarized by parameter and grade ([Table 89](#)).

Descriptive statistics including mean, median, standard deviation, maximum, and minimum values and change from baseline by time point, for all and each chemistry and hematology laboratory parameter will be summarized by actual baseline ordinal score and treatment arm ([Table 51](#) and [Table 90](#)). Changes in chemistry and hematology laboratory values will be presented in line graphs over time with median, Q1 and Q3 plotted by actual baseline ordinal score and treatment arm ([Figure 34](#)).

Listings will provide a complete listing of individual chemistry and hematology laboratory results with applicable reference ranges ([Listing 23](#)).

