	Day 5	Baricitinib + PBO + RDV	x	x	X	x	x	x	x		
		PBO + Dexamethasone + RDV	x	x	X	x	x	x	x		
	Day 8	Baricitinib + PBO + RDV	x	x	X	x	x	x	x		
		PBO + Dexamethasone + RDV	x	x	X	x	x	x	x		
	Day 11	Baricitinib + PBO + RDV	x	x	X	x	x	x	x		
		PBO + Dexamethasone + RDV	x	x	X	x	x	x	x		
	Day 15	Baricitinib + PBO + RDV	x	x	X	x	x	x	x		
		PBO + Dexamethasone + RDV	x	x	X	x	x	x	x		
	Day 29	Baricitinib + PBO + RDV	x	x	X	x	x	x	x		
		PBO + Dexamethasone + RDV	x	x	X	x	x	x	x		
	Maximum Severity Post Baseline		x	x	X	x	x	x	x		
			x	x	X	x	x	x	x		
Each parameter will be summarized individually similar to the above...											
The “Max Post Baseline” rows indicate the maximum severity experienced by each subject at any time point post baseline, including unscheduled assessments and assessments beyond Day 29.											
N = Number of subjects in the As Treated Population											

Programming Note: Vitamin D, D-dimer and CRP results are not included in this table. Include all lab parameters that are being graded in this table.

Table 89: Treatment-Emergent Laboratory Abnormalities - As Treated Population, Actual Baseline Ordinal Score of 5 or 6

Laboratory Parameter	Maximum Post Baseline Grade	Baricitinib + PBO + RDV (N=X)			PBO + Dexamethasone + RDV (N=X)		
		N	n	%	N	n	%
Any Parameter	1	x	x	x	x	x	x
	2	x	x	X	x	x	x
	3	x	x	X	x	x	x
	4	x	x	X	x	x	x
	Any Grade	x	x	X	x	x	x
Continue for all graded parameters							
N = number of subjects in the As Treated Population with any post-baseline data available for the specified Lab Parameter.							
n = number of subjects in the As Treated Population with treatment emergent abnormalities for the specified Lab Parameter.							
A treatment emergent laboratory abnormality is defined as a post-baseline abnormal value with a severity grade greater than at baseline.							

Table 90: Summary Statistics of Laboratory Results by Parameter, Study Visit Day, and Treatment Group – As Treated Population, Actual Baseline Ordinal Score 5 or 6

Laboratory Parameter	Study Visit Day	Treatment Group	Absolute					Change from Baseline				
			N	Mean	95% CI	Median	Min, Max	N	Mean	95% CI	Median	Min, Max
Parameter 1	Baseline	Baricitinib + PBO + RDV	x	xx.x	xx.x, xx.x	xx.x	xx.x, xx.x	---	---	---	---	---
		PBO + Dexamethasone + RDV	x	xx.x	xx.x, xx.x	xx.x	xx.x, xx.x	---	---	---	---	---
	Day 3	Baricitinib + PBO + RDV	x	xx.x	xx.x, xx.x	xx.x	xx.x, xx.x	x	xx.x	xx.x, xx.x	xx.x	xx.x, xx.x

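### Subjects whose INR is left ungraded stay in the denominators of Tables 88 and 89 and dilute the INR abnormality rate; separately, the INR adverse event rule contradicts itself for an isolated elevation

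*SAP*

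**What the plan says.** INR is a named laboratory safety endpoint (SAP Section 3.2) and is among the parameters to which Section 9.6 applies the DAIDS grading table.

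**Grading.** Section 15.2.3 notes that the DAIDS INR grades are meant for subjects not on anticoagulants. It continues: "As many of the subjects will be on anticoagulant therapy", these subjects' "INR values will not be graded". It gives no figure for how many that is.

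**Tables.** The Table 89 footnote (Appendix 1) reads "N = number of subjects in the As Treated Population with any post-baseline data available for the specified Lab Parameter". Its numerator requires a post-baseline grade higher than the baseline grade. Table 88 counts Grade 3 and Grade 4 results and defines N as the As Treated Population. Neither table removes ungraded subjects for INR.

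**AE reporting.** The second bullet of Section 15.2.3 covers subjects not on anticoagulants, and names LMWH in the same clause. For an INR of 2.0 × ULN or more, its two sentences run "grade 3+) then an AE for INR should be reported. Note that abnormal INR values should be reported as part of a clinical syndrome", and the second ends "and not reported as a separate AE".

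**The concern.** There are two separate defects, and they affect different outputs.

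1. **Laboratory-grade tables (88 and 89).** A subject without a grade can never enter the numerator but is kept in N. The table therefore presents a subject who was not assessed as one who was assessed and found normal. By the SAP's own account this is not a rare case. Anticoagulant use can also change after randomization, so the ungraded share need not be the same in both arms.

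2. **AE tables.** A site with an isolated INR elevation and no syndrome has two instructions with opposite results. Grade 3/4 AE counts (Tables 60, 61 and 76) and the composite of death, SAE or Grade 3/4 AE (Section 3.3.14, Table 77) then depend on which sentence the site followed.

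The LMWH wording feeds into both. The AE bullet appears to treat LMWH users like subjects not on anticoagulants, but the grading sentence does not say so.

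**Working it through.** **Plan's own figure.** The SAP states no INR rate, no anticoagulant share and no INR event count, so there is nothing to reproduce. What follows is algebra with labelled assumptions.

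**Inputs**
- a: share of subjects with INR data who are ungraded. Not given; assumed range 20% to 90%.
- r: abnormality rate among gradable subjects. Not given; assumed 5%, with 2% and 10% as alternatives.
- M: subjects per arm. 1500 / 2 = 750, from the planned total in SAP Section 5 and assuming equal arms. M cancels out of the rates.

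**Dilution**
- Gradable subjects = M(1 − a)
- Subjects with an abnormality = r · M(1 − a)
- Displayed rate = r · M(1 − a) / M = r(1 − a)
- Rate on gradable subjects = r

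Example with r = 5% and a = 60%: gradable = 750 × 0.40 = 300; events = 0.05 × 300 = 15; displayed 15/750 = 2.0%; on gradable subjects 15/300 = 5.0%.

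| a | displayed, r = 2% | displayed, r = 5% | displayed, r = 10% |
|---|---|---|---|
| 20% | 1.6% | 4.0% | 8.0% |
| 40% | 1.2% | 3.0% | 6.0% |
| 60% | 0.8% | 2.0% | 4.0% |
| 80% | 0.4% | 1.0% | 2.0% |
| 90% | 0.2% | 0.5% | 1.0% |

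This treats each subject as either gradable or ungraded throughout and assumes that everyone in N has INR data. Table 88's N, read literally, also includes subjects without an INR at the time point, which would dilute its rate further.

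**Comparison of arms**
- Same a in both arms: the factor (1 − a) cancels in the ratio. A difference is multiplied by (1 − a), so a true 4-point difference shows as 3.2, 1.6 or 0.4 points at a = 20%, 60% or 90%.
- Different a, equal true rates of 5%: with a = 60% and 70%, 0.05 × 0.40 = 2.0% against 0.05 × 0.30 = 1.5%, ratio 1.33. With a = 50% and 70%, 2.5% against 1.5%, ratio 1.67. No true difference exists in either case.

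**The AE rule, sentence by sentence** (subject not on anticoagulants, INR 2.0 × ULN or more)

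| Situation | First sentence | Second sentence |
|---|---|---|
| Part of a clinical syndrome | AE | AE, recorded as the syndrome |
| Isolated, no syndrome | AE | No separate AE, and no syndrome to carry it |

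The sentences can be reconciled in the first row but not in the second. Section 15.2.2 on glucose shows the contrast: the cases it covers each have one outcome.

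**LMWH.** If the bullet is a carve-out, LMWH users are held to the grade 3 threshold for AE reporting, while the general grading sentence, taken alone, leaves them ungraded. If LMWH falls under the negation in that clause, the bullet excludes them. The choice also moves a, because LMWH users are either inside or outside the ungraded group.

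**The case against.** The case on the other side is substantial.

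- *The rate is not wrong in itself.* It can be read as a rate among all subjects with INR data, and with balanced anticoagulant use the ratio between arms is intact. Tables 88 and 89 print no between-arm difference or p-value. This stands. The defect is that nothing tells the reader that part of N could never contribute an event.
- *The values are still shown.* Table 90 summarises INR values and changes from baseline regardless of grade, Listing 23 gives every result, and Section 15.2.3 still has anticoagulated subjects at 3.0 × ULN or more reported in the context of a syndrome. This also stands, so a reader who infers that most of any INR signal is hidden goes too far. That inference would also need a value of a that the SAP does not supply.
- *The AE conflict is narrow.* It bites only for isolated elevations. A reader might infer that it also moves the rates in Tables 88 and 89. It does not, because those are graded from laboratory values.
- *LMWH is probably a carve-out.* That is the natural reading. The fault is that the grading sentence does not repeat it.

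A further inference is tempting: that Day 29 INR is misgraded because Section 9.1.2 reviews "medications taken within 7 days prior to enrollment through approximately Day 15 or early termination", while Section 9.6 says "Clinical safety laboratory adverse events are collected Day 1, 3, 5, 8, 11 and Day 15 and 29 if able to return to clinic". The documents do not support this. The SAP names no source for anticoagulant status. Section 9.8 has medication use recorded over the study without a Day 15 limit, and the Listing 9 notes flag ongoing drugs, so these can be carried forward. Nothing ties site AE reporting to the medication form. Leaving Day 29 INR ungraded on this ground would discard safety data.

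**Conclusion.** The point holds in two limited parts. First, as the footnotes are written, the INR abnormality rates in Tables 88 and 89 are diluted by the factor (1 − a) relative to subjects who could be graded. At an assumed r of 5% that means 4.0% displayed at a = 20% and 1.0% at a = 80%. A false contrast between arms arises only if a differs by arm. Both r and a are assumptions, so the direction is certain but the size is not. Second, Section 15.2.3 gives opposite AE instructions for an isolated elevation off anticoagulants, and leaves the grading of LMWH users to inference. The documents do not show that any reported INR rate will be wrong by a known amount. The primary and secondary efficacy analyses are untouched.

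**What to change.** 1. In Tables 88 and 89, set the INR denominator to subjects with at least one gradable INR: at the time point for the by-visit rows, and post-baseline for the maximum-grade rows and Table 89. Footnote the number ungraded per arm.
2. Reconcile the two AE sentences in Section 15.2.3 into one rule that covers the isolated elevation explicitly. Which sentence should prevail is for the sponsor to decide.
3. State once whether LMWH users count as anticoagulated, and apply that to both grading and AE reporting.

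**Cost.** Items 1 and 3 need SAP wording and a gradable-INR flag. The downside is a smaller INR denominator and hence less precise rates. Item 2 may cost more: Section 15.3 records that all subjects were already enrolled when version 2.0 was written, so a clarified rule could require sites to re-check INR events already reported or omitted.

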15.3. Changes to the SAP from Version 1.0 to Version 2.0

The below summarizes the changes made to the SAP from version 1.0 to version 2.0.

- As described in Section 15.1, the primary analysis was updated to use a weighted test statistic.
- As described in Section 15.2, text was added to describe reporting of AEs for eGFR, Creatinine, Glucose and INR.
- It was decided that the Day 60 analyses would be included in the final study report, rather than an addendum. The SAP was amended to include data through Day 60.
- At the time of the SAP update, all subjects were enrolled and there was only one known stratification error where a subject was neither ordinal score 5 nor 6 at baseline. Since only one subject fell into the “other” category in SAP version 1.0, tables were updated to include the one stratification error in the overall summaries but exclude the subject from subgroup analyses and modeling with adjustments for baseline strata. The SAP was left flexible enough to handle any additional stratifications errors identified prior to database lock.
- Modeling including baseline strata was updated to only be run based on handling the baseline ordinal score as continuous since there are only two levels included (i.e., baseline ordinal score 5 or 6).
- SAP version 1.0 table title “Infections by Treatment Group” was updated to be “Culture Results by Treatment Group and AE Severity”. Additional tables of infections by MedDRA preferred term were added.
- Section 3.3.3, the following sentence was removed: “Subjects who are randomized but do not initiate treatment will be censored at time 0.” Additionally, the following sentence was added: “Subjects not completing Day 29 or discharged to hospice or other end-of-life care prior to Day 29 with a death date unknown but completing Day 60 will be reviewed by the blinded Endpoint Review Committee to assess whether the Day 60 data impacts handling of the subject for the Day 29 timepoint.”
- Throughout the document:
 - Typos and errors introduced via copying/pasting language from other sections were corrected.
 - Clinical Status was updated to be “Ordinal Score” in the tables for consistency with language used in prior ACTT clinical study reports.
 - Titles for tables and figures were updated to include “by Day 29”, where applicable, to distinguish from Day 60 outcomes.

17. LISTING OF TABLES, FIGURES, AND LISTINGS

Table, figure, and listing shells are presented in [Appendix 1](#), [Appendix 2](#), and [Appendix 3](#).

The formatting of the final version of a table, figure, or listing may differ from what is presented in the shell or the presentation of the results may be changed, however the key content will remain unchanged. Additional summaries/data points may be included in the final version of a table, figure, or listing, as well. Additional tables, figures, and listings may be generated to supplement the planned output.

Table 87: VTEs by Treatment Group – As Treated Population, Actual Baseline Ordinal Score 5 or 6.....	132
Table 88: Abnormal Laboratory Results of Grade 3 or 4 by Parameter, Maximum Severity, Time Point, and Treatment Group – As Treated Population, Actual Baseline Ordinal Score of 5 or 6.....	133
Table 89: Treatment-Emergent Laboratory Abnormalities - As Treated Population, Actual Baseline Ordinal Score of 5 or 6	134
Table 90: Summary Statistics of Laboratory Results by Parameter, Study Visit Day, and Treatment Group – As Treated Population, Actual Baseline Ordinal Score 5 or 6	135

Table 2: Ineligibility Summary of Screen Failures

Inclusion/Exclusion Category	Inclusion/Exclusion Criterion	n ^a	% ^b
All Subjects	Total number of subjects failing any eligibility criterion or were eligible but not randomized	X	100
Inclusion and Exclusion	Number of subjects failing any eligibility criterion	X	xx
Inclusion	Any inclusion criterion	X	xx
	[inclusion criterion 1]	X	xx
	[inclusion criterion 2]	X	xx
	[inclusion criterion 3]	X	xx
Exclusion	Any exclusion criterion	X	xx
	[exclusion criterion 1]	X	xx
	[exclusion criterion 2]	X	xx
	[exclusion criterion 3]	X	xx
Eligible but Not Enrolled		X	xx

^a More than one criterion may be marked per subject.^b Denominator for percentages is the total number of screen failures.

Programming Note: Subjects who are eligible but not randomized will be counted in the denominator.

Table 3: Analysis Population Eligibilities by Treatment Group and Actual Baseline Ordinal Score

Analysis Population	Inclusion / Reason for Exclusion	Baricitinib + PBO + RDV			PBO + Dexamethasone + RDV		
		Baseline Ordinal Score 5	Baseline Ordinal Score 6	All Subjects ^d	Baseline Ordinal Score 5	Baseline Ordinal Score 6	All Subjects ^d
	n	n	n	n	n	n	n
Intent-to-Treat Population (Randomized Strata) ^a	Included in Population	x	x	x	x	x	x
Modified Intent-to-Treat Population (Actual Baseline Clinical Status) ^b	Included in Population	x	x	x	x	x	x
As Treated Population ^c	Included in Population	x	x	x	x	x	x
	Excluded from Population	x	x	x	x	x	x
	Did Not Receive Dose of Baricitinib/Placebo	x	x	x	x	x	x
	Did Not Receive Dose of Dexamethasone/Placebo						

^a Counts are the numbers of subjects randomized to the specified treatment group with the randomized baseline ordinal score.^b Counts are the numbers of subjects randomized to the specified treatment group with the actual baseline ordinal score.^c Counts are the numbers of subjects who received the specified treatment with the actual baseline ordinal score.^d [X] additional subjects are included in the ‘All Subjects’ column that were enrolled with a baseline ordinal score of 4. [Include as applicable]**Programming Notes:**

If at least one subject received the incorrect treatment, then a footnote will be added which reads “XX subject[s] [was/were] randomized to [insert randomized treatment] but was administered [insert actual treatment]. In addition, a row under “Included in Population” and “Excluded from Population” will be added for the As Treated Population section with the label “Randomized to [insert randomized treatment] but administered [insert actual treatment].”

Table 4: Subject Disposition by Treatment Group and Actual Baseline Ordinal Score – mITT Population

Subject Disposition	Baricitinib + PBO + RDV (N=X)						PBO + Dexamethasone + RDV (N=X)						All Subjects (N = X)					
	Baseline Ordinal Score 5 (N=X)		Baseline Ordinal Score 6 (N=X)		All Subjects (N=X) ^a		Baseline Ordinal Score 5 (N=X)		Baseline Ordinal Score 6 (N=X)		All Subjects (N=X) ^a		Baseline Ordinal Score 5 (N=X)		Baseline Ordinal Score 6 (N=X)		All Subjects (N=X) ^a	
	n/N	%	n/N	%	n/N	%	n/N	%	n/N	%	n/N	%	n/N	%	n/N	%	n/N	%
Randomized	x/x	100	x/x	100	x/x	100	x/x	100	x/x	100	x/x	100	x/x	100	x/x	100	x/x	100
Terminated Early from Study	x/x	xx	x/x	xx	x/x	xx	x/x	xx	x/x	xx	x/x	xx	x/x	xx	x/x	xx	x/x	xx
Discharged from Hospital	x/x	xx	x/x	xx	x/x	xx	x/x	xx	x/x	xx	x/x	xx	x/x	xx	x/x	xx	x/x	xx
Died During Follow-up	x/x	xx	x/x	xx	x/x	xx	x/x	xx	x/x	xx	x/x	xx	x/x	xx	x/x	xx	x/x	xx
Completed Follow-up (Study Day 1) – Hospitalized Subjects in Study	x/x	xx	x/x	xx	x/x	xx	x/x	xx	x/x	xx	x/x	xx	x/x	xx	x/x	xx	x/x	xx
Ordinal Scale Data Available	x/x	xx	x/x	xx	x/x	xx	x/x	xx	x/x	xx	x/x	xx	x/x	xx	x/x	xx	x/x	xx
Safety Laboratory Blood Draw	x/x	xx	x/x	xx	x/x	xx	x/x	xx	x/x	xx	x/x	xx	x/x	xx	x/x	xx	x/x	xx
OP Swab Collection	x/x	xx	x/x	xx	x/x	xx	x/x	xx	x/x	xx	x/x	xx	x/x	xx	x/x	xx	x/x	xx
PCR Assays Blood Draw	x/x	xx	x/x	xx	x/x	xx	x/x	xx	x/x	xx	x/x	xx	x/x	xx	x/x	xx	x/x	xx
Secondary Research Blood Draw	x/x	xx	x/x	xx	x/x	xx	x/x	xx	x/x	xx	x/x	xx	x/x	xx	x/x	xx	x/x	xx
Repeat for Days 3, 5, 8, 11																		
Completed Follow-up (Study Day 15) – All Subjects in Study	x/x	xx	x/x	xx	x/x	xx	x/x	xx	x/x	xx	x/x	xx	x/x	xx	x/x	xx	x/x	xx
Ordinal Scale Data Available	x/x	xx	x/x	xx	x/x	xx	x/x	xx	x/x	xx	x/x	xx	x/x	xx	x/x	xx	x/x	xx
Safety Laboratory Blood Draw	x/x	xx	x/x	xx	x/x	xx	x/x	xx	x/x	xx	x/x	xx	x/x	xx	x/x	xx	x/x	xx
OP Swab Collection	x/x	xx	x/x	xx	x/x	xx	x/x	xx	x/x	xx	x/x	xx	x/x	xx	x/x	xx	x/x	xx
Secondary Research Blood Draw	x/x	xx	x/x	xx	x/x	xx	x/x	xx	x/x	xx	x/x	xx	x/x	xx	x/x	xx	x/x	xx
Completed Follow-up (Study Day 22) – All Subjects in Study	x/x	xx	x/x	xx	x/x	xx	x/x	xx	x/x	xx	x/x	xx	x/x	xx	x/x	xx	x/x	xx
Ordinal Scale Data Available	x/x	xx	x/x	xx	x/x	xx	x/x	xx	x/x	xx	x/x	xx	x/x	xx	x/x	xx	x/x	xx
Completed Follow-up (Study Day 29) – All Subjects in Study	x/x	xx	x/x	xx	x/x	xx	x/x	xx	x/x	xx	x/x	xx	x/x	xx	x/x	xx	x/x	xx
Ordinal Scale Data Available	x/x	xx	x/x	xx	x/x	xx	x/x	xx	x/x	xx	x/x	xx	x/x	xx	x/x	xx	x/x	xx

Subject Disposition	Baricitinib + PBO + RDV (N=X)						PBO + Dexamethasone + RDV (N=X)						All Subjects (N = X)			
	Baseline Ordinal Score 5 (N=X)		Baseline Ordinal Score 6 (N=X)		All Subjects (N=X) ^a		Baseline Ordinal Score 5 (N=X)		Baseline Ordinal Score 6 (N=X)		All Subjects (N=X) ^a		Baseline Ordinal Score 5 (N=X)		Baseline Ordinal Score 6 (N=X)	
	n/N	%	n/N	%	n/N	%	n/N	%	n/N	%	n/N	%	n/N	%	n/N	%
Safety Laboratory Blood Draw	x/x	xx	x/x	xx	x/x	xx	x/x	xx	x/x	xx	x/x	xx	x/x	xx	x/x	xx
OP Swab Collection	x/x	xx	x/x	xx	x/x	xx	x/x	xx	x/x	xx	x/x	xx	x/x	xx	x/x	xx
Secondary Research Blood Draw	x/x	xx	x/x	xx	x/x	xx	x/x	xx	x/x	xx	x/x	xx	x/x	xx	x/x	xx

N = Number of subjects randomized and in study for visits 1, 15, 22 and 29 and the number of subjects hospitalized and in study for visits 3, 5, 8 and 11. Subjects that died or terminated from the study on or prior to the study visit are not included in the denominators.

^a[X] additional subjects are included in the 'All Subjects' column that were enrolled with a baseline ordinal score of 4. [Include as applicable]

Table 5: Subject Status at Study Termination by Treatment Group and Actual Baseline Ordinal Score – mITT Population

Baseline Ordinal Score	Category	Status at Termination	Baricitinib + PBO + RDV			PBO + Dexamethasone + RDV		
			N	n	%	N	n	%
All Subjects ^a	Any Status	Any Status	x	x	x	x	x	x
	Recovery	Recovered	x	x	x	x	x	x
		Not Recovered	x	x	x	x	x	x
	Hospitalization	Hospitalized	x	x	x	x	x	x
		Not Hospitalized	x	x	x	x	x	x
	Relative to Day 15	Prior to Day 15	x	x	x	x	x	x
		On or After Day 15	x	x	x	x	x	x
Continue for Baseline Ordinal Score 5, 6

N = Number of subjects in the mITT Population with the baseline ordinal score.
 Status at termination based on the time of the last ordinal score collection.
^a[X] additional subjects are included in the 'All Subjects' column that were enrolled with a baseline ordinal score of 4. [Include as applicable]

Table 6: Baricitinib / PO Placebo Exposure by Treatment Group and Actual Baseline Ordinal Score – mITT Population

	Baricitinib + PBO + RDV (N = X)			PBO + Dexamethasone + RDV (N = X)		
	Baseline Ordinal Score 5 (N=X)	Baseline Ordinal Score 6 (N=X)	All Subjects (N=X) ^a	Baseline Ordinal Score 5 (N=X)	Baseline Ordinal Score 6 (N=X)	All Subjects (N=X) ^a
Number of Doses Received						
N	X	X	X	X	X	X
Mean (SD)	X.X (X.X)	X.X (X.X)	X.X (X.X)	X.X (X.X)	X.X (X.X)	X.X (X.X)
Median	X	X	X	X	X	X
Q1, Q3	X, X	X, X	X, X	X, X	X, X	X, X
Min, Max	X, X	X, X	X, X	X, X	X, X	X, X
Number of Subjects by Doses Received						
1 Dose	X	X	X	X	X	X
2 Doses	X	X	X	X	X	X
3 Doses	X	X	X	X	X	X
4 Doses	X	X	X	X	X	X
5 Doses	X	X	X	X	X	X
6 Doses	X	X	X	X	X	X
7 Doses	X	X	X	X	X	X
8 Doses	X	X	X	X	X	X
9 Doses	X	X	X	X	X	X
10 Doses	X	X	X	X	X	X
11 Doses	X	X	X	X	X	X
12 Doses	X	X	X	X	X	X
13 Doses	X	X	X	X	X	X
14 Doses	X	X	X	X	X	X
Number of Subjects Treatment Temporarily Held	X	X	X	X	X	X
Number of Subjects by Reason for Hold	X	X	X	X	X	X
[Reason 1]	X	X	X	X	X	X
[Reason 2]	X	X	X	X	X	X
Etc...	X	X	X	X	X	X
Number of Subjects Discontinuing Treatment	X	X	X	X	X	X
Number of Subjects by Reason for Discontinuation	X	X	X	X	X	X
[Reason 1]	X	X	X	X	X	X
[Reason 2]	X	X	X	X	X	X
Etc...	X	X	X	X	X	X

^a[X] additional subjects are included in the 'All Subjects' column that were enrolled with a baseline ordinal score of 4. [Include as applicable]

Table 7: Dexamethasone / IV Placebo Exposure by Treatment Group and Actual Baseline Ordinal Score – mITT Population

	Baricitinib + PBO + RDV (N = X)			PBO + Dexamethasone + RDV (N = X)		
	Baseline Ordinal Score 5 (N=X)	Baseline Ordinal Score 6 (N=X)	All Subjects (N=X) ^a	Baseline Ordinal Score 5 (N=X)	Baseline Ordinal Score 6 (N=X)	All Subjects (N=X) ^a
Number of Doses Received						
N	x	x	x	x	x	x
Mean (SD)	x.x (x.x)	x.x (x.x)	x.x (x.x)	x.x (x.x)	x.x (x.x)	x.x (x.x)
Median	x	x	x	x	x	x
Q1, Q3	x, x	x, x	x, x	x, x	x, x	x, x
Min, Max	x, x	x, x	x, x	x, x	x, x	x, x
Number of Subjects who Received Dexamethasone Prior to Enrollment	x	x	x	x	x	x
Number of Subjects by Doses Received						
1 Dose	x	x	x	x	x	x
2 Doses	x	x	x	x	x	x
3 Doses	x	x	x	x	x	x
4 Doses	x	x	x	x	x	x
5 Doses	x	x	x	x	x	x
6 Doses	x	x	x	x	x	x
7 Doses	x	x	x	x	x	x
8 Doses	x	x	x	x	x	x
9 Doses	x	x	x	x	x	x
10 Doses	x	x	x	x	x	x
Number of Subjects Discontinuing Treatment	x	x	x	x	x	x
Number of Subjects by Reason for Discontinuation	x	x	x	x	x	x
[Reason 1]	x	x	x	x	x	x
[Reason 2]	x	x	x	x	x	x
Etc...	x	x	x	x	x	x

^a[X] additional subjects are included in the 'All Subjects' column that were enrolled with a baseline ordinal score of 4. [Include as applicable]

Table 8: Remdesivir Exposure by Treatment Group and Actual Baseline Ordinal Score – mITT Population

	Baricitinib + PBO + RDV (N = X)			PBO + Dexamethasone + RDV (N = X)		
	Baseline Ordinal Score 5 (N=X)	Baseline Ordinal Score 6 (N=X)	All Subjects (N=X) ^a	Baseline Ordinal Score 5 (N=X)	Baseline Ordinal Score 6 (N=X)	All Subjects (N=X) ^a
Number of Doses Received						
N	x	x	x	x	x	x
Mean (SD)	x.x (x.x)	x.x (x.x)	x.x (x.x)	x.x (x.x)	x.x (x.x)	x.x (x.x)
Median	x	x	x	x	x	x
Q1, Q3	x, x	x, x	x, x	x, x	x, x	x, x
Min, Max	x, x	x, x	x, x	x, x	x, x	x, x
Number of Subjects who Received RDV Prior to Enrollment	x	x	x	x	x	x
Number of Subjects by Doses Received						
1 Dose	x	x	x	x	x	x
2 Doses	x	x	x	x	x	x
3 Doses	x	x	x	x	x	x
4 Doses	x	x	x	x	x	x
5 Doses	x	x	x	x	x	x
6 Doses	x	x	x	x	x	x
7 Doses	x	x	x	x	x	x
8 Doses	x	x	x	x	x	x
9 Doses	x	x	x	x	x	x
10 Doses	x	x	x	x	x	x
Number of Subjects Treatment Temporarily Held	x	x	x	x	x	x
Number of Subjects by Reason for Hold	x	x	x	x	x	x
[Reason 1]	x	x	x	x	x	x
[Reason 2]	x	x	x	x	x	x
Etc...	x	x	x	x	x	x
Number of Subjects Discontinuing Treatment	x	x	x	x	x	x
Number of Subjects by Reason for Discontinuation	x	x	x	x	x	x
[Reason 1]	x	x	x	x	x	x
[Reason 2]	x	x	x	x	x	x
Etc...	x	x	x	x	x	x

^a [X] additional subjects are included in the 'All Subjects' column that were enrolled with a baseline ordinal score of 4. [Include as applicable]

Table 9: Subjects Reporting Prior Remdesivir Treatment by Actual Baseline Ordinal Score and Treatment Group – mITT Population

Prior RDV Treatment Summary	Baricitinib + PBO + RDV (N=X)			PBO + Dexamethasone + RDV (N=X)		
	Baseline Ordinal Score 5 (N=X)	Baseline Ordinal Score 6 (N=X)	All Subjects (N=X) ^a	Baseline Ordinal Score 5 (N=X)	Baseline Ordinal Score 6 (N=X)	All Subjects (N=X) ^a
Received RDV Treatment Prior to Enrollment – n (%)	x (x)	x (x)	x (x)	x (x)	x (x)	x (x)
Number of Doses of RDV Received Prior to Enrollment						
Number of Subjects with Number of Doses Available	x	x	x	x	x	x
Mean (STD)	x.x (x.x)	x.x (x.x)	x.x (x.x)	x.x (x.x)	x.x (x.x)	x.x (x.x)
Median	x.x	x.x	x.x	x.x	x.x	x.x
IQR	x.x, x.x	x.x, x.x	x.x, x.x	x.x, x.x	x.x, x.x	x.x, x.x
Range (Min, Max)	x.x, x.x	x.x, x.x	x.x, x.x	x.x, x.x	x.x, x.x	x.x, x.x

^a [X] additional subjects are included in the 'All Subjects' column that were enrolled with a baseline ordinal score of 4. [Include as applicable]

Table 10: Subjects Reporting Prior Baricitinib Treatment by Actual Baseline Ordinal Score and Treatment Group – mITT Population

Prior RDV Treatment Summary	Baricitinib + PBO + RDV (N=X)			PBO + Dexamethasone + RDV (N=X)		
	Baseline Ordinal Score 5 (N=X)	Baseline Ordinal Score 6 (N=X)	All Subjects (N=X) ^a	Baseline Ordinal Score 5 (N=X)	Baseline Ordinal Score 6 (N=X)	All Subjects (N=X) ^a
Received baricitinib Treatment Prior to Enrollment – n (%)	x (x)	x (x)	x (x)	x (x)	x (x)	x (x)
Number of Doses of Baricitinib Received Prior to Enrollment						
Number of Subjects with Number of Doses Available	x	x	x	x	x	x
Mean (STD)	x.x (x.x)	x.x (x.x)	x.x (x.x)	x.x (x.x)	x.x (x.x)	x.x (x.x)
Median	x.x	x.x	x.x	x.x	x.x	x.x
IQR	x.x, x.x	x.x, x.x	x.x, x.x	x.x, x.x	x.x, x.x	x.x, x.x
Range (Min, Max)	x.x, x.x	x.x, x.x	x.x, x.x	x.x, x.x	x.x, x.x	x.x, x.x

^a[X] additional subjects are included in the 'All Subjects' column that were enrolled with a baseline ordinal score of 4. [Include as applicable]

Table 11: Subjects Reporting Prior Dexamethasone Treatment by Actual Baseline Ordinal Score and Treatment Group – mITT Population

Prior RDV Treatment Summary	Baricitinib + PBO + RDV (N=X)			PBO + Dexamethasone + RDV (N=X)		
	Baseline Ordinal Score 5 (N=X)	Baseline Ordinal Score 6 (N=X)	All Subjects (N=X) ^a	Baseline Ordinal Score 5 (N=X)	Baseline Ordinal Score 6 (N=X)	All Subjects (N=X) ^a
Received Dexamethasone Treatment Prior to Enrollment – n (%)	x (x)	x (x)	x (x)	x (x)	x (x)	x (x)
Number of Doses of Dexamethasone Received Prior to Enrollment						
Number of Subjects with Number of Doses Available	x	x	x	x	x	x
Mean (STD)	x.x (x.x)	x.x (x.x)	x.x (x.x)	x.x (x.x)	x.x (x.x)	x.x (x.x)
Median	x.x	x.x	x.x	x.x	x.x	x.x
IQR	x.x, x.x	x.x, x.x	x.x, x.x	x.x, x.x	x.x, x.x	x.x, x.x
Range (Min, Max)	x.x, x.x	x.x, x.x	x.x, x.x	x.x, x.x	x.x, x.x	x.x, x.x

^a[X] additional subjects are included in the 'All Subjects' column that were enrolled with a baseline ordinal score of 4. [Include as applicable]

Table 12: Day 60 Subject Disposition by Treatment Group and Actual Baseline Ordinal Score – mITT Population

Subject Disposition	Baricitinib + PBO + RDV (N=X)				PBO + Dexamethasone + RDV (N=X)				All Subjects (N=X)				All Subjects (N=X)					
	Ordinal Score 5 (N=X)		Ordinal Score 6 (N=X)		All Subjects ^a (N = X)		Ordinal Score 5 (N=X)		Ordinal Score 6 (N=X)		All Subjects ^a (N = X)		Ordinal Score 5 (N=X)		Ordinal Score 6 (N=X)		All Subjects ^a (N = X)	
	n	%	n	%	n	%	n	%	n	%	n	%	n	%	n	%	n	%
Visit Occurred	x	xx	x	xx	x	xx	x	xx	x	xx	x	xx	x	xx	x	xx	x	xx
Type of Visit ^b	x	xx	x	xx	x	xx	x	xx	x	xx	x	xx	x	xx	x	xx	x	xx
Inpatient/In-person Visit																		
Phone Visit																		
Chart Review																		
Subject Deceased After the Day 29 Visit Window																		
Was the Subject Seen by a Doctor, Outside a Hospital Re-Admission after Day 29/Last Study Contact?																		
Was the Subject Re-Admitted after Day 29/Last Study Contact?																		
If Seen by a Doctor or Re-Admitted after Day 29/Last Study Contact, Was the Reason Due to a Worsening or Exacerbated Pre-Existing Condition?																		

N = Number of subjects in the mITT Population.
n = Number of subjects meeting the criteria.
^a[X] additional subjects are included in the 'All Subjects' column that were enrolled with a baseline ordinal score of 4. [Include as applicable]
^bPercentage based on the number of subjects with a visit. Visits may be conducted by more than one method (e.g., inpatient and chart review).

Table 13: Distribution of Subject Specific Protocol Deviations by Category, Type, Treatment Group, and Actual Baseline Ordinal Score - mITT Population

Category	Deviation Type	Baricitinib + PBO + RDV (N=X)						PBO + Dexamethasone + RDV (N=X)						All Subjects (N=X)					
		Baseline Ordinal Score 5 (N=X)		Baseline Ordinal Score 6 (N=X)		All Subjects (N=X) ^a		Baseline Ordinal Score 5 (N=X)		Baseline Ordinal Score 6 (N=X)		All Subjects (N=X) ^a		Baseline Ordinal Score 5 (N=X)		Baseline Ordinal Score 6 (N=X)		All Subjects (N=X) ^a	
		# of Subj.	# of Dev.	# of Subj.	# of Dev.	# of Subj.	# of Dev.	# of Subj.	# of Dev.	# of Subj.	# of Dev.	# of Subj.	# of Dev.	# of Subj.	# of Dev.	# of Subj.	# of Dev.	# of Subj.	# of Dev.
Eligibility/ randomization	Any type	X	X	X	X	X	X	X	X	X	X	X	X	X	X	X	X	X	X
	Did not meet inclusion criterion	X	X	X	X	X	X	X	X	X	X	X	X	X	X	X	X	X	X
	Met exclusion criterion	X	X	X	X	X	X	X	X	X	X	X	X	X	X	X	X	X	X
	ICF not signed prior to study procedures	X	X	X	X	X	X	X	X	X	X	X	X	X	X	X	X	X	X
	Other	X	X	X	X	X	X	X	X	X	X	X	X	X	X	X	X	X	X
Treatment administration schedule	Any type	X	X	X	X	X	X	X	X	X	X	X	X	X	X	X	X	X	X
	Out of window visit	X	X	X	X	X	X	X	X	X	X	X	X	X	X	X	X	X	X
	Missed visit/visit not conducted	X	X	X	X	X	X	X	X	X	X	X	X	X	X	X	X	X	X
	Missed treatment administration	X	X	X	X	X	X	X	X	X	X	X	X	X	X	X	X	X	X
	Delayed treatment administration	X	X	X	X	X	X	X	X	X	X	X	X	X	X	X	X	X	X
	Other	X	X	X	X	X	X	X	X	X	X	X	X	X	X	X	X	X	X
Follow-up visit schedule	Any type	X	X	X	X	X	X	X	X	X	X	X	X	X	X	X	X	X	X
	Out of window visit	X	X	X	X	X	X	X	X	X	X	X	X	X	X	X	X	X	X

Category	Deviation Type	Baricitinib + PBO + RDV (N=X)						PBO + Dexamethasone + RDV (N=X)						All Subjects (N=X)					
		Baseline Ordinal Score 5 (N=X)		Baseline Ordinal Score 6 (N=X)		All Subjects (N=X) ^a		Baseline Ordinal Score 5 (N=X)		Baseline Ordinal Score 6 (N=X)		All Subjects (N=X) ^a		Baseline Ordinal Score 5 (N=X)		Baseline Ordinal Score 6 (N=X)		All Subjects (N=X) ^a	
		# of Subj.	# of Dev.	# of Subj.	# of Dev.	# of Subj.	# of Dev.	# of Subj.	# of Dev.	# of Subj.	# of Dev.	# of Subj.	# of Dev.	# of Subj.	# of Dev.	# of Subj.	# of Dev.	# of Subj.	# of Dev.
	Missed visit/visit not conducted	X	X	X	X	X	X	X	X	X	X	X	X	X	X	X	X	X	X
	Other	X	X	X	X	X	X	X	X	X	X	X	X	X	X	X	X	X	X
Protocol procedure/assessment	Any type	X	X	X	X	X	X	X	X	X	X	X	X	X	X	X	X	X	X
	Incorrect version of ICF signed	X	X	X	X	X	X	X	X	X	X	X	X	X	X	X	X	X	X
	Blood not collected	X	X	X	X	X	X	X	X	X	X	X	X	X	X	X	X	X	X
	Oropharyngeal swab not collected	X	X	X	X	X	X	X	X	X	X	X	X	X	X	X	X	X	X
	Other specimen not collected	X	X	X	X	X	X	X	X	X	X	X	X	X	X	X	X	X	X
	Specimen result not obtained	X	X	X	X	X	X	X	X	X	X	X	X	X	X	X	X	X	X
	Required procedure not conducted	X	X	X	X	X	X	X	X	X	X	X	X	X	X	X	X	X	X
	Required procedure done incorrectly	X	X	X	X	X	X	X	X	X	X	X	X	X	X	X	X	X	X
	Study product temperature excursion	X	X	X	X	X	X	X	X	X	X	X	X	X	X	X	X	X	X
	Specimen temperature excursion	X	X	X	X	X	X	X	X	X	X	X	X	X	X	X	X	X	X
	Stratification error	X	X	X	X	X	X	X	X	X	X	X	X	X	X	X	X	X	X
	Other	X	X	X	X	X	X	X	X	X	X	X	X	X	X	X	X	X	X

Category	Deviation Type	Baricitinib + PBO + RDV (N=X)						PBO + Dexamethasone + RDV (N=X)						All Subjects (N=X)					
		Baseline Ordinal Score 5 (N=X)		Baseline Ordinal Score 6 (N=X)		All Subjects (N=X) ^a		Baseline Ordinal Score 5 (N=X)		Baseline Ordinal Score 6 (N=X)		All Subjects (N=X) ^a		Baseline Ordinal Score 5 (N=X)		Baseline Ordinal Score 6 (N=X)		All Subjects (N=X) ^a	
		# of Subj.	# of Dev.	# of Subj.	# of Dev.	# of Subj.	# of Dev.	# of Subj.	# of Dev.	# of Subj.	# of Dev.	# of Subj.	# of Dev.	# of Subj.	# of Dev.	# of Subj.	# of Dev.	# of Subj.	# of Dev.
Treatment administration	Any type	x	x	x	x	x	x	x	x	x	x	x	x	x	x	x	x	x	x
	Required procedure done incorrectly	x	x	x	x	x	x	x	x	x	x	x	x	x	x	x	x	x	x
	Study product temperature excursion	x	x	x	x	x	x	x	x	x	x	x	x	x	x	x	x	x	x
	Other	x	x	x	x	x	x	x	x	x	x	x	x	x	x	x	x	x	x
Blinding policy/procedure	Any type	x	x	x	x	x	x	x	x	x	x	x	x	x	x	x	x	x	x
	Treatment unblinded	x	x	x	x	x	x	x	x	x	x	x	x	x	x	x	x	x	x
	Other	x	x	x	x	x	x	x	x	x	x	x	x	x	x	x	x	x	x

^a[X] additional subjects are included in the 'All Subjects' column that were enrolled with a baseline ordinal score of 4. [Include as applicable]

Table with similar format:

Table 14: Distribution of Major Subject Specific Protocol Deviations by Category, Type, Treatment Group, and Actual Baseline Ordinal Score – mITT Population

Table 15: Mechanical Ventilation-free Survival by Day 29 by Treatment Group and Actual Baseline Ordinal Score

Analysis Population	Treatment Group	Actual Baseline Ordinal Score	Number Subjects requiring Mechanical Ventilation by Day 29	Number Subjects Dying by Day 29	Day 29 Mechanical Ventilation-Free Survival		HR		P-value
					Estimate	95% CI	Estimate	95% CI	
mITT Population	Baricitinib + PBO + RDV (N=X)	5	x	x	x.x	x.x, x.x	x.xx	x.xx, x.xx	--
	PBO + Dexamethasone + RDV (N=X)		x	x	x.x	x.x, x.x			
	Baricitinib + PBO + RDV (N=X)	6	x	x	x.x	x.x, x.x	x.xx	x.xx, x.xx	--
	PBO + Dexamethasone + RDV (N=X)		x	x	x.x	x.x, x.x			
	Baricitinib + PBO + RDV (N=X)	Baseline Clinical Status 5 or 6	x	x	x.x	x.x, x.x	x.xx	x.xx, x.xx	0.xxx
	PBO + Dexamethasone + RDV (N=X)		x	x	x.x	x.x, x.x			
	Baricitinib + PBO + RDV (N=X)	Any Baseline Ordinal Score	x	x	x.x	x.x, x.x	x.xx	x.xx, x.xx	--
	PBO + Dexamethasone + RDV (N=X)		x	x	x.x	x.x, x.x			

Repeat for the As Treated Population and ITT population.

N= Number of subjects in the specified treatment group, actual baseline ordinal score, and analysis population.

n = Number of subjects.

Mechanical Ventilation-Free Survival are Kaplan-Meier Estimates at Day 29 study visit

HR is the ratio of the hazard of mechanical ventilation or death in each treatment group estimated from the Cox model. The ratio is to PBO + Dexamethasone + RDV to Baricitinib + PBO + RDV.

HRs for the 'combined ordinal score groups' are the hazard ratio from the stratified Cox Model.

